# 7 STATISTICAL METHODOLOGY AND STATISTICAL ANALYSES

# 7.1 STATISTICAL METHODS

Means, medians, and standard deviations will be provided for continuous variables when performing descriptive analysis of continuous data. Numbers and percentages will be provided for dichotomous and polychotomous variables when performing descriptive analysis of categorical data. The proportion of CR/CRi achieved will be compared across the number of salvage therapies prior to InO initiation with respective 95% confidence interval. Kaplan-Meier survival curve will be drawn for longest time from initiation of InO to date of data extracted. Similarly survival curve will be drawn for relaspse free survival. Median survival or restricted mean survival time will be reported across the number of salvage therapies.

# 7.2 STATISTICAL ANALYSES

The distribution demographics variables like age and sex will be summarized by mean  $\pm$ SD and frequency (%) respectively. The prevalence of complete remission or complete remission with incomplete hematological recovery following treatment with InO will be reported with 95% confidence interval. Further these prevalence will be estimated for the

number of salvage therapies  $(0, 1, \ge 2)$  received before InO initiation.6 months or 12 months restricted mean remission free time will be estimated with 95% CI for both complete remission or complete remission with incomplete hematological recovery. The Kaplan-Meier curves of remission free survival will be drawn if a sufficient representation observed across the number of salvage therapies  $(0, 1, \ge 2)$  received before InO initiation. The restricted mean remission free time with 95% CI will be estimated for categories of number of salvage therapies. Restricted mean/median survival time will also be estimated with 95% CI. The Kaplan-Meier overall survival curve will also be drawn.

Other secondary endpoints like MRD negativity following initiation of InO or dosage pattern, concomitant medications, cause of death , occurrence of Grade 3/4 treatment-related adverse events in lung/cardiac/kidney/liver etc. following InO initiation and CR/CRi in EMD/LBL will also summarized by frequency and percentage and dration of response(DOR), no of patients who proceeded to transplant, total during study treatment and post HSCT will be summarized my median and interquartile range. restricted relapse-free-survival time will also be estimated with 95% CI if data permits for all patients and patients with or without follow-up HSCT.

Due to non-probability sampling technique, the extrapolation of the results will be restricted to the population that matches with sample characteristics only. Magnitude of the measure of any characteristics will be prioritised over statistical interpretation. However, interpretation of the result will be in a qualitative sense even though the related feature is compared numerically owing to descriptive nature of the study.

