#### This PACL makes the following changes:

	izer		
3	6. MILESTONES	Change in Milestones- Planned Date	Start of data collection - 13 February 2023 End of data collection - 05 July 2023 Final Study report - 10 October 2023
4	9. RESEARCH METHODS 9.3 Study size	Sample size changed to 32 subjects	Sample size is changed to 32 subjects
5	11. MANAGEMENT AND REPORTING OF ADVERSE EVENTS/ADVERSE REACTIONS 12. SAFETY REPORTING	To clarify the adverse event reporting requirements for structured and unstructured data components. Also, to correct the inconsistency with the protocol template language.	The last 2 paragraphs of Section 11 should be moved to the beginning of Section 12, Adding a subheading "12.1 Structured Data Analysis", under which the 2 paragraphs are pasted and revised. In addition, add a second sub- heading "12.2 Human Review of Unstructured Data" above the original content of Section 12.

In the event that this protocol requires substantial changes that apply globally to all sites in the future or regulatory authorities request that these changes be incorporated into an updated protocol, the administrative changes described in this letter will be incorporated into the amended protocol.

Please inform your institutional review board/ ethics committee of these changes, as required.

Sincerely, [name]

cc: NI study master file

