# **Study population**

This is a descriptive study and there is no prior hypothesis specified, therefore a formal sample size calculation is not required. The sample size of approximately 55 patients has been based on the number of patients expected to be available at these 7-10 sites that individually treated the largest number of patients with InO.

The study will include information on approximately 55 patients as per the availability of data from 7-10 sites.

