# 3.2 STATISTICAL DECISION RULES

As no specified hypothesis will be tested, no decision rule are required to specify. However, for any assessment of external validity for a suitable population accepted false positive rate will be 5%. For any such validation only two sided test will be performed.

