# 7.2.2 Analyses of endpoint

The following tables and figures will be generated for the analysis of endpoints.

- 1. The distribution of demographics characteristics (mean ±SD for age and frequency and percentage for sex)
- 2. MRD negativity following initiation of InO (frequency and percentage)
- 3. Dosage pattern (frequency and percentage)
- 4. Cause of death (frequency and percentage)
- 5. Occurrence of Grade 3/4 treatment-related adverse events in lung/cardiac/kidney/liver etcfollowing InO initiation (frequency and percentage)
- 6. CR/CRi in EMD/LBL (frequency and percentage)
- 7. Duration of response (DOR) (Median and Interquartile Range (IQR))
- 8. No of patients who proceeded to transplant (Median and IQR)
- 9. Total during study treatment and post HSCT (Median and IQR)
- 10. Restricted remission free time with 95% confidence interval for both complete remission and complete remission with incomplete hematological recovery.

- 11. Restricted remission free time with 95% confidence interval for both complete remission and complete remission with incomplete hematological recovery stratified by the number of salvage therapies  $(0, 1, \ge 2)$  received before InO initiation
- 12. Restricted mean overall survival time with 95% CI.
- 13. Restricted relapse-free-survival with 95% CI for all patients and patients with or without follow-up HSCT.

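### MRD negativity, Grade 3/4 events and EMD/LBL response get no confidence interval, and transplant and the apparent VOD line get a median and IQR; all are yes/no outcomes needing n/N, % and an exact 95% CI

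*SAP*

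**What the plan says.** **Outcomes with an interval.** SAP 7.2 says that CR/CRi prevalence "following treatment with InO will be reported with 95% confidence interval", and SAP 7.1 extends this to the comparison across salvage categories. SAP 7.2 also attaches 95% intervals to restricted mean remission-free time, to restricted mean or median survival time and, data permitting, to restricted relapse-free survival time.

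**Outcomes without one.** For MRD negativity, Grade 3/4 treatment-related events and response in EMD/LBL, SAP 7.2 has the outcomes "following InO initiation and CR/CRi in EMD/LBL will also summarized by frequency and percentage". SAP 7.2.2 repeats this in items 2, 5 and 6, for example "MRD negativity following initiation of InO (frequency and percentage", and section 8 carries the same items. SAP 7.1 makes numbers and percentages the default for categorical data. SAP 7.2.1 (safety analyses) is marked not applicable, and Appendix 2 adds no method.

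**Outcomes with a median and IQR.** SAP 7.2, 7.2.2 item 8 and section 8 assign these statistics to the number of patients who go to transplant. Item 9 assigns them to a total during treatment and after HSCT, without naming what is totalled. The endpoint list in SAP section 5 uses that same split for the VOD rate, so item 9 is apparently VOD.

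**Size.** Item 4 of the Protocol Administrative Change Letter states: "Sample size is changed to 32 subjects". The SAP still reads: "The sample size of approximately 55 patients has been based on the number of patients expected to be available". Neither figure rests on a precision target; the SAP says "a formal sample size calculation is not required".

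**The concern.** The plan treats CR/CRi as an estimate whose uncertainty must be shown, and the other binary outcomes as bare percentages. It gives no reason for the difference. With 32 patients or fewer, sampling error on those percentages is large. It is least visible at 0% and 100%, where the percentage gives no hint of spread.

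The median and IQR are a separate fault. For a yes/no variable they take only a few values and barely respond to the rate, so tables 8 and 9 as specified would not convey how many patients were transplanted or had VOD.

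At stake is how the results can be read. SAP section 2 describes Indian real-world data on InO monotherapy as limited, with a single study of 8 patients, so these percentages are likely to be quoted.

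**Working it through.** **Inputs**
- N = 32 (Change Letter, item 4); N = 55 (SAP, Study population) as a sensitivity value.
- Two-sided 95% intervals, as for CR/CRi. This is in line with SAP 3.2, which fixes a 5% error rate and two-sided tests for any external-validity assessment.
- Phase 3 figures cited in SAP section 2: 41% to HSCT, 81% response, 78% MRD-negative among responders.
- The documents do not give the number of EMD/LBL, MRD-assessed or transplanted patients. These are assumptions below.

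The plan has no figure of its own to reproduce for these outcomes.

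**Method.** Exact (Clopper-Pearson) limits for x events in n: lower = Beta quantile (0.025; x, n−x+1), upper = Beta quantile (0.975; x+1, n−x). For x = 0 the upper limit is 1 − 0.025^(1/n). For x = n the lower limit is 0.025^(1/n).

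**Whole cohort (for example Grade 3/4 events)**
- 0/32: upper limit 1 − 0.025^(1/32) = 10.9%. The Wilson method gives 10.7%.
- 1/32 = 3.1% (0.1 to 16.2%).
- 3/32 = 9.4% (2.0 to 25.0%).
- Chance of no event in 32: 0.95^32 = 0.194 if the true rate is 5%; 0.90^32 = 0.034 if it is 10%.
- At the SAP's 55, 0/55 has an upper limit of 6.5%.

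**HSCT split (assumed).** 41% of 32 is 13.1, so about 13 transplanted and 19 not. 0/13: upper limit 1 − 0.025^(1/13) = 24.7%. 0/19: upper limit 17.6%.

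**EMD/LBL, all patients responding (assumed size 2 to 8)**

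| x/n | Exact lower limit |
|---|---|
| 2/2 | 15.8% |
| 3/3 | 29.2% |
| 5/5 | 47.8% |
| 8/8 | 63.1% |

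For 3/3 the Wilson lower limit is 43.9%. The choice of method matters at this size, but the interval is wide either way.

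**MRD negativity (assumed counts).** Protocol section 3 restricts the denominator to assessed patients, and SAP section 6 rules out imputation, so n is at most 32. 81% of 32 is about 26 responders, and 78% of 26 is about 20. 20/26 = 76.9% (56.4 to 91.0%). If only 15 are assessed, 12/15 = 80.0% (51.9 to 95.7%).

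**Median and IQR of a yes/no variable at N = 32.** Code the event as 1 and otherwise 0.
- With 0 to 7 events (0 to 21.9%), at least 25 of the 32 values are 0, so the median is 0 and the IQR is 0 to 0.
- With 9 to 15 events (28.1 to 46.9%), the median is 0 and the IQR is 0 to 1 throughout.

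A cohort with no VOD and one with 7 cases would therefore give the same table entry.

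**The case against.** The strongest defence is that this is a descriptive study with no hypothesis and no decision rule on these outcomes. Counts will be printed, so a reader can derive the interval. SAP 7.2 also restricts extrapolation to patients resembling the sample and asks for qualitative interpretation. Much of this stands: no data are lost, and how firmly readers will take a bare 0% or 100% is a guess. It does not remove the point. The same descriptive SAP plans intervals for CR/CRi, and an interval needs no hypothesis. The caveats concern representativeness, not sampling precision. SAP 7.2 also ranks the magnitude of a measure above its statistical interpretation, which gives the bare percentage more weight.

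Three stronger readings are tempting, and the documents do not support them:
- **That harms are shown without uncertainty while benefits have it.** MRD negativity and EMD/LBL response are benefits and also lack intervals. The actual division is between the primary endpoint with the time-based summaries and the other categorical secondary outcomes.
- **That these outcomes have the smallest denominators in the study.** Grade 3/4 events are defined first in all patients (SAP section 5). The salvage strata of the primary endpoint subdivide the cohort and do get intervals.
- **That survival in general gets intervals.** This is true of restricted mean or median times. The 6- and 12-month survival rates in SAP section 5 have no stated interval.

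A further fair objection is that an exact interval reflects binomial error only. Sampling is non-probability, and patients who did not complete one cycle are excluded, so an upper limit such as 10.9% could be misread as a ceiling on risk. The fix has to answer this.

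**Conclusion.** The point holds as a gap in reporting, modest in consequence and cheap to close. No section of either document supplies an interval for MRD negativity, Grade 3/4 events or EMD/LBL response. The median and IQR for transplant and the apparent VOD line are the wrong statistics.

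The whole-cohort figures rest only on N = 32: no event is compatible with a rate up to 10.9%, and a true 5% rate is missed altogether 19% of the time. At 55 the first figure falls to 6.5%, so the conclusion does not depend on which sample size is used. The subgroup figures (3/3 down to 29%, 0/13 up to 24.7%) rest on assumed sizes and only illustrate the scale. Reading item 9 as VOD is an inference from the matching split in the endpoint list.

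**What to change.** 1. In SAP 7.2, in 7.2.2 items 2, 5 and 6, and in the matching items of section 8, report n/N, percentage and an exact (Clopper-Pearson) two-sided 95% interval. Include cells at 0 and 100%. Do this overall and within the HSCT split where that split is planned.
2. In SAP 7.2, in 7.2.2 items 8 and 9, and in section 8, replace the median and IQR with n/N, percentage and an exact 95% interval for patients transplanted and for patients with VOD. Name VOD in item 9.
3. Add a sentence stating that these intervals reflect sampling error only. They do not cover selection from non-probability sampling or from excluding patients who did not complete one cycle.

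The cost is SAP wording and a column in existing tables, with no new data. The downside is that wide intervals become visible. Without the sentence in step 3, an upper limit could be taken as a ceiling on risk.

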## 9.1. Study design /Setting

The study is classified as a Non-interventional study (NIS) secondary data collection- unstructured review with sites/investigators.

R/R B-cell ALL patients who are 18 years old at the time of InO initiation and those who received the drug outside of clinical trials will be evaluated.

Data will be collected retrospectively from patients hospital medical records (paper-based ) by members of the direct care team (investigators). We intend to have 7- 10 sites across India using InO monotherapy including patients with both private purchase and compassionate use to reach a cohort of approximately 55. If needed, more sites will be enrolled to meet the target cohort. Data will be reviewed and analyzed from all the sites.

Medical records will be reviewed to collect demographic, patient-related, disease-related, and clinical outcome data. These patients will be evaluated for response (CR/CRi), MRD status, duration of remission (DOR), Dosage patterns, Rate of transplant, Overall survival in all patients including Survival rate at 6 months and 12 months in transplanted patients & non transplanted patients, Relapse free survival (RFS), Rate of VOD (Total, during study treatment and post HSCT if any patient underwent HSCT), safety/tolerability, Other adverse effects (including hematological toxicities and raised liver enzymes), No of cycles to achieve MRD negativity in responders & CR/CRi in EMD/LBL.

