#### 9.1.4. Secondary endpoints

- MRD Negativity following initiation of Ino
- Number of cycles of InO needed to attain CR/CRi
- DOR
- Dosage pattern: InO doses, dose modifications, and the number of cycles of treatment;
- Concomitant medications
- Rate of transplant (No of patients who proceeded to transplant)
- Survival rate at 6 months & 12 months (transplanted patients & non transplanted patients, in both who achieved CR/CRi and MRD negativity)
- Cause of death
- Relapse-free-survival; in all patients and patients with or without follow-up HSCT.
- Rate of VOD (Total, during study treatment and post HSCT, if any patient underwent HSCT) in transplanted & non transplanted patients.
- Occurrence of Grade 3/4 treatment-related adverse events in lung/cardiac/kidney/liver etc following InO initiation; in all patients and patients with or without follow-up HSCT & hematological toxicities
- CR/CRi in EMD/LBL

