# 2.1 STUDY DESIGN

The study is classified as a Non-interventional study (NIS) secondary data collectionunstructured review with sites/investigators.

R/R B-cell ALL patients who are  $\geq 18$  years old at the time of InO initiation and those who received the drug outside of clinical trials will be evaluated.

Data will be collected retrospectively from patients hospital medical records (paper-based) by members of the direct care team (investigators). We intend to have 7-10 sites across India using InO monotherapy including patients with both private purchase and compassionate use to reach a cohort of approximately 55 patients. If needed, more sites will be enrolled to meet the target cohort. Data will be reviewed and analyzed from all the sites.

Medical records will be reviewed to collect demographic, patient-related, disease-related, and clinical outcome data. These patients will be evaluated for response (CR/CRi), MRD status, duration of remission (DOR), dosage patterns, rate of transplant, survival time for all patients including survival rate at 6 months and 12 months in transplanted patients & non transplanted patients, Relapse free survival (RFS) time, Rate of veno-occlusive disease (VOD) (total during study treatment and post HSCT if any patient underwent HSCT), safety/tolerability, Other adverse effects (including hematological toxicities and raised liver enzymes), Number of cycles to achieve MRD negativity in responders & CR/CRi in Extramedullary disease / lymphoblastic lymphoma (EMD/LBL).

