# Secondary objective

The secondary objective is to explore the presence/occurrence of other factors along with primary outcome, listed as follows

- MRD Negativity following initiation of Ino
- Number of cycles of InO needed to attain CR/CRi
- Duration of response(DOR)
- Dosage pattern: InO doses, dose modifications, and the number of cycles of treatment
- Concomitant medications

- *Rate of transplant (No of patients who proceeded to transplant)*
- Survival rate (transplanted patients & non transplanted patients, in both who achieved *CR/CRi* and *MRD* negativity)
- Cause of death
- Relapse-free-survival in all patients and patients with or without follow-up HSCT.
- *Rate of VOD (Total during study treatment and post HSCT, if any patient underwent HSCT) in transplanted & non transplanted patients.*
- Occurrence of Grade 3/4 treatment-related adverse events in lung/cardiac/kidney/liver etc following InO initiation; in all patients and patients with or without follow-up HSCT & hematological toxicities
- CR/CRi in EMD/LBL

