#### Secondary endpoints

- MRD Negativity following initiation of Ino
- Number of cycles of InO needed to attain CR/CRi
- DOR
- Dosage pattern: InO doses, dose modifications, and the number of cycles of treatment
- *Concomitant medications*
- *Rate of transplant (No of patients who proceeded to transplant)*
- Survival rate at 6 months & 12 months (transplanted patients & non transplanted patients, in both who achieved CR/CRi and MRD negativity)
- Cause of death
- *Relapse-free-survival in all patients and patients with or without follow-up HSCT.*
- *Rate of VOD (Total, during study treatment and post HSCT, if any patient underwent HSCT) in transplanted & non transplanted patients.*
- Occurrence of Grade 3/4 treatment-related adverse events in lung/cardiac/kidney/liver etc following InO initiation; in all patients and patients with or without follow-up HSCT & hematological toxicities
- CR/CRi in EMD/LBL

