#### 8 LIST OF TABLES AND TABLE SHELLS

- 1. The distribution of demographics characteristics (mean±SD for age and frequency and percentage for sex)
- 2. MRD Negativity following initiation of InO(frequency and percentage)
- 3. Dosage pattern(frequency and percentage)
- 4. Cause of death (frequency and percentage)
- 5. Occurrence of Grade 3/4 treatment-related adverse events in lung/cardiac/kidney/liver etc following InO initiation (frequency and percentage)
- 6. CR/CRi in EMD/LBL (frequency and percentage)
- 7. Duration of response(DOR) (Median and IQR)
- 8. No of patients who proceeded to transplant (Median and IQR)
- 9. Total during study treatment and post HSCT (Median and IQR)
- 10. Restricted remission free time with 95% confidence interval for both complete remission and complete remission with incomplete hematological recovery.
- 11. Restricted remission free time with 95% confidence interval for both complete remission and complete remission with incomplete hematological recovery stratified by the number of salvage therapies  $(0, 1, \ge 2)$  received before InO initiation
- 12. Restricted mean overall survival time with 95% CI.
- 13. Restricted relapse-free-survival with 95% CI for all patients and patients with or without follow-up HSCT

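### SAP 7.2 and table items 8 and 9 give median and IQR to the yes/no transplant endpoint and to an unnamed item that is very probably the VOD rate

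*SAP*

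**What the plan says.** The analysis text in SAP 7.2 puts two items in the same clause as duration of response: "no of patients who proceeded to transplant, total during study treatment and post HSCT will be summarized my median and interquartile range". The table lists carry this forward. Item 8 in SAP 7.2.2 reads "No of patients who proceeded to transplant (Median and IQR", and item 9 in SAP 8 reads "Total during study treatment and post HSCT (Median and IQR". Both items appear in the same form in both lists.

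The endpoint definitions describe something else. Among the secondary endpoints in SAP 5, transplant is "Rate of transplant (No of patients who proceeded to transplant". The SAP secondary objectives contain "Rate of VOD (Total during study treatment and post HSCT, if any patient underwent HSCT) in transplanted & non transplanted patients", and SAP 2.1 has "Rate of veno-occlusive disease (VOD) (total during study treatment and post HSCT if any patient underwent HSCT". Protocol 9.1.4 gives the same endpoint with a comma after the first word in the brackets: "Rate of VOD (Total, during study treatment and post HSCT, if any patient underwent HSCT) in transplanted & non transplanted patients".

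The general rules are clear. SAP 7.1 gives numbers and percentages to dichotomous variables, and Protocol 9.5 gives frequency and percentage to all qualitative outcomes. SAP 5.1 describes the other secondary outcomes as mostly binary.

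**The concern.** There are two faults.

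- **Wrong type of summary.** Each patient either proceeds to transplant or does not. A median and IQR do not summarise that, and the item-specific instruction contradicts the general rule one section earlier. SAP 7.2 itself handles comparable yes/no endpoints (MRD negativity, grade 3/4 treatment-related events, CR/CRi in EMD/LBL) by frequency and percentage.
- **No event named.** Item 9 does not say what is being totalled. VOD is not named anywhere from SAP 7.1 to SAP 8, and SAP 7.2.1 marks safety analyses as not applicable. If item 9 is not VOD, no listed output names VOD at all, although it is a stated secondary endpoint.

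At stake is whether the listed tables can deliver two secondary endpoints of the protocol. The programmer would have to depart from the text to report the transplant rate, and cannot tell from item 9 what to count.

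**Working it through.** **Inputs.** N = 32 from item 4 of the protocol administrative change letter; N of about 55 from SAP 2.1 (study population). The plan states no expected transplant or VOD rate for this cohort, so there is no planned figure to reproduce. The check covers every possible count instead.

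**Step 1: what the planned summary prints.** Take a variable with k ones and N − k zeros. Compute the median and quartiles by linear interpolation; counting sorted values from 0, the quantile p sits at position p(N − 1).

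For N = 32 the positions are 7.75, 15.5 and 23.25. For N = 55 they are 13.5, 27 and 40.5.

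| Printed result, median (IQR) | N = 32: counts k | N = 55: counts k |
|---|---|---|
| 0 (0-0) | 0-7 (0-21.9%) | 0-13 (0-23.6%) |
| 0 (0-1) | 9-15 (28.1-46.9%) | 15-27 (27.3-49.1%) |
| 1 (0-1) | 17-23 (53.1-71.9%) | 28-40 (50.9-72.7%) |
| 1 (1-1) | 25-32 (78.1-100%) | 42-55 (76.4-100%) |
| Interpolated values | 8, 16, 24 | 14, 41 |

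At N = 32 the four main outputs cover 8 + 7 + 7 + 8 = 30 of 33 possible counts. At N = 55 they cover 14 + 13 + 13 + 14 = 54 of 56. Five other quantile definitions move the boundaries by at most one patient.

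**Step 2: a concrete case.** The background sections cite a 41% transplant rate in the InO arm of the phase 3 trial. Used only as an illustration, that is 13/32 = 40.6% or 23/55 = 41.8%. The planned table would print 0 (0-1) at either size, as it would for 9/32 = 28.1%. Reported as n/N (%) with an exact 95% CI, the same data give 40.6% (23.7 to 59.4) or 41.8% (28.7 to 55.9).

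**Step 3: what item 9 is.** Its wording repeats the bracketed text that follows the VOD rate in the SAP secondary objectives and in SAP 2.1. Protocol 11 also treats VOD as a number of participants. VOD is therefore the natural reading, but the documents do not state it.

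**Step 4: how many VOD figures.** Protocol 9.1, Protocol 9.1.4 and the SAP 5 endpoint list have a comma after the opening word, giving three quantities: total, during treatment and post HSCT. SAP 2.1 and the SAP secondary objectives omit it. That reads as two quantities, or on another reading as one combined total.

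**Step 5: why the denominator must be stated, if item 9 is VOD.** As an assumption, let 9 to 15 of 32 patients be transplanted and 2 of them have VOD after HSCT. Then 2/15 = 13.3% to 2/9 = 22.2% of transplanted patients are affected, but only 2/32 = 6.25% of everyone.

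**Step 6: other outputs.** Item 13 splits relapse-free survival by HSCT and could show the group sizes, but SAP 7.2 makes that analysis conditional on the data allowing it. Item 5 could catch some VOD among grade 3/4 treatment-related liver events, but not the VOD rate. No other listed table or figure gives either rate.

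**The case against.** The strongest reply is that this would correct itself. Transplant is defined as a rate, Protocol 9.5 covers all qualitative outcomes, and Protocol 9.6.2 obliges the vendor to analyse the data as the protocol describes. A programmer holding a 0/1 field would see that the summary is misapplied. The study tests no hypothesis, and the data are collected either way. Protocol 11 already counts VOD by participants, and item 13 carries no condition in the table lists themselves.

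Much of this is fair, and it limits the weight of the point. It does not remove it. The instruction appears in the analysis text and in both table lists, so using percentages means overriding the specific text. No general rule supplies the event missing from item 9. A median across sites, or of a time, would make sense statistically, but the documents define no such variable for either item. Item 13 is a survival analysis and reports no VOD.

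Three parts of the reply stand:

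- The comma and the denominator example are secondary.
- The documents do not specify denominators, so those proposed below are a recommendation.
- If item 9 is VOD, the statements in SAP 5.2 and 7.2.1 that safety endpoints and analyses do not apply sit awkwardly beside it.

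**Conclusion.** The concern holds. For transplant, the specified summary is wrong for the type of variable and contradicts SAP 7.1 and Protocol 9.5. Most possible rates collapse to four printed results (30 of 33 counts at N = 32, 54 of 56 at N = 55), so the rate cannot be recovered from the table. The conclusion is the same at either sample size.

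Item 9 is unusable as written because it names no event. That it breaks the number-and-percentage rule depends on the inference that it is VOD, which the sponsor must confirm.

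The arithmetic assumes per-patient yes/no data. The primary endpoint is not affected, and duration of response (item 7), being a duration, is outside this point. It should be corrected before the tables are programmed.

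**What to change.** Amend SAP 7.2 and items 8 and 9 in SAP 7.2.2 and SAP 8:

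1. **Item 8.** Report patients proceeding to transplant as n/N (%), with N = all analysed patients. Because SAP 6 uses available data only, show how many have unknown status.
2. **Item 9.** Once the sponsor confirms that VOD is meant, name it and report n/N (%): total and during study treatment (N = all analysed), and post HSCT (N = transplanted). Give the breakdown by transplant status that Protocol 9.1.4 and SAP 5 call for, with N = each group; the post-HSCT row applies only to transplanted patients.
3. **SAP 7.2 sentence.** Move both items out of the median/IQR clause and into the list summarised by frequency and percentage. An exact 95% CI is an optional addition.
4. **VOD wording.** Align SAP 2.1 and the SAP secondary objectives with Protocol 9.1 and 9.1.4 and SAP 5, so that the number of VOD figures is unambiguous.

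The cost is wording in three SAP places and a comma in two more. No endpoint changes and no new data are needed, since Protocol 9.1.4 already lists both endpoints.
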